8. PHARMACEUTICAL INFORMATION

A list of the adverse events and potential risks associated with the investigational or commercial agents administered in this study can be found in Section 7.2.

TGR-1202

[figure not shown]
Classification:	Phosphatidylinositol-3-Kinase (PI3K) Delta Inhibitor
Formulation:	See Investigator Brochure
Mode of Action:	Irreversibly inhibits activity of the Class I Delta isoform of PI3K
How Supplied:	TGR-1202: 200 mg tablets
Storage:	Store at 25°C. Excursions permitted 15°C to 30°C.
Stability:	Retest dates will be provided periodically by Sponsor.
Route of Administration:	Oral
Packaging:	TGR-1202 is provided in HDPE bottles each containing 30 tablets and a silica gel canister as a desiccant.
Availability:	TGR-1202 is available from TG Therapeutics.

9. PHARMACOKINETIC/PHARMACODYNAMIC STUDIES

Pharmacokinetic (PK) Studies

Up to 5 ml of blood will be collected in Lithium Heparin tubes for isolation of plasma at PreTreatment on C1D1, and 4h post-treatment on C1D1, C1D15, C2D15 and C4D15 (Figure 2).

Figure 2. PK schedule

Blood samples will be stored on ice until centrifuged. After centrifuge, plasma will be stored in polypropylene screw top tube at -70°C until evaluation by liquid chromatography.

Pharmacodynamics Studies

Collection of specimens

Participation in correlative studies is mandatory for all patients. In addition to the mandatory correlative studies for all patients, there will also be optional correlative studies, which will be performed under a separate section of the informed consent form.

Missing 4 doses or more 1 week prior to the planned biopsy on Cycle 2 Day 15 could render that patient ineligible for biopsy, but that decision will be made at the discretion of the treating physician and Study PI.

Mandatory correlative studies include the following:

For PK studies:

1. Collection of blood at Pre-treatment (approx. 3 ml).

2. Collection of blood at 4h post-treatment on C1D1, C1D15, C2D15, and C4D15 (total approx. 12 ml).

For PD studies:

1. Collection of blood at Pre-Treatment.

Collection of blood at 4h post-treatment on C1D1, C1D15, C2D15 and C4D15. The studies will include T cell panel such as T-reg, expression of CD47 and PD-L1, cytokines such as IL-10 and IL-12, and PI3K targeting.

2. Collection of tumor tissues, blood cells, and buccal fibroblasts pre-treatment and 4-8h posttreatment on C2D15.

The studies will include whole exome sequencing, and the levels/activity of c-Myc, 4E-BP1, CK1, and PI3K.

[figure not shown]
[figure not shown]
Missing 4 doses or more 1 week prior to the planned biopsy on C2D15 could render that patient ineligible for biopsy, but that decision will be made at the discretion of the treating physician and Study PI.

Optional correlative studies are listed below:

Collection of tumor tissues and buccal fibroblasts 4-8h post-treatment on C4D15, at Progression of Disease, and at End of Treatment.

The studies will include whole exome sequencing, and the levels/activity of c-Myc, 4E-BP1, CK1, and PI3K.

Figure 3. PD schedule

The patient will have the option of checking off boxes within the main consent form for this study to indicate consent or denial for the optional studies as explained above.

Fine Needle Aspirations (FNA): A series of FNAs will be performed on palpable tumors in consenting patients as a function of drug exposure.

Tumor Tissue Biopsies: The biopsies will be performed by a surgeon or an interventional radiologist, as appropriate. If multiple lymph nodes are available, the safest lymph node will be selected. A cytopathologist will evaluate the biopsy for tumor cells microscopically at the time of the biopsy. Correlative studies will be performed on de-identified tissue samples. Tissue will be labeled only with the protocol-specific unique identifier.

Bone Marrow Biopsy: a bone marrow aspirate and biopsy will be performed pre-treatment if necessary to determine the stage of the disease.

Handling of Specimens

Specimens required for clinical diagnosis will be submitted to Pathology per standard patient care practice.

Research specimens will be handled as explained below:

- Blood will be processed to isolate the serum and mononuclear cells. The specimens may then be used immediately for correlative studies such as flow cytometry or stored for future studies in bulk with all patient samples. Stored samples will be either frozen at -80 degrees or refrigerated at 4 degrees Celsius.
- Bone marrow and other tissue aspirate samples will be processed to isolate the mononuclear cells enriched for viable lymphoma cells. The specimens may then be used for correlative studies such as flow cytometry immediately or stored for future studies in bulk with all patient samples.
- Samples from core biopsy (e.g. bone marrow, skin, lymph nodes or other lymphoid tissue) may be snap frozen in a dry ice/alcohol bath or liquid nitrogen, or processed for the isolation of viable lymphoma cells.
- Fibroblasts will be isolated from buccal swabs, and frozen or refrigerated as above.
- Cellular samples will be used immediately or snap frozen, depending on the type of correlative studies. For example, *ex vivo* pharmacological studies require fresh isolated lymphoma. mRNA and DNA may be extracted from frozen or fixed cellular or tissue specimens.

Biomarker studies

A major goal of this study is to determine the genetic, and biochemical heterogeneity in the follicular lymphoma cells, and discover the effects of distinct cellular and molecular alterations on patient response to TGR-1202. To this end, we will perform the following studies using patient samples:

- Conduct DNA and RNA sequencing and gene expression studies on samples before and after treatment with TGR-1202.
- Compare and contrast the effects of TGR-1202 on mRNA translation in normal fibroblasts and lymphocytes versus lymphoma cells from the same patient, using the state of the art technology of ribosome profiling.
- Compare and contrast the effects of TGR-1202 on the mTOR signaling in normal fibroblasts and lymphocytes versus lymphoma cells from the same patient, using Western blot and IHC staining.
- Develop an *in vitro* system to test responsiveness to TGR-1202 in primary lymphoma cells isolated fresh from patients.

- Test synergy of TGR-1202 with drugs targeting pathways that interact with PI3K, using lymphoma cell lines and primary FL cells from patients on study
- Determine the effects of TGR-1202 on cytokine production in the blood of patients treated on study
- Develop an *in vivo* model of FL by directly implanting FL cells from patient biopsies into mice patient derived xenograft (PDX) model.

10. STUDY CALENDAR

Baseline evaluations are to be conducted as indicated in the table below, prior to start of protocol therapy. In the event that the patient's condition is deteriorating, laboratory evaluations should be repeated within 48 hours prior to initiation of the next cycle of therapy.

(All study assessments allow a +/- 3 day window)

Cycle		1				2+				
	Screening	D1	D8	D15	D22 ⁿ	D1	D15	End of treatment ^k	End of Study (4 weeks after last dose)	Follow-up ^m
Eligibility, safety monitoring, efficacy										
Informed Consent	X ^a									
Demographics	X ^a									
Medical History	X ^a									

EKG	X ^a								
Concurrent Medications	X ^b	X ^c	X	X	X	X		X	X
Physical exam	X ^b	X ^e	X	X	X	X		X	X
Vital Signs, weight	X ^b	X	X	X	X	X		X	X
Performance Status	X ^b	X	X	X	X	X		X	X
CBC w/ differential	X ^b	X ^e	X	X	X	X		X	X
Chemistries ^{c,g}	X ^b	X ^e	X	X	X	X		X	X
Coagulation tests	X ^b								
Creatinine clearance	X ^b								
Serum \square -hCG ^d	X ^b	X							
CT (or PET/CT)	X ^a					X ^f			X ^f
Bone Marrow Biopsy	X ^a					X ^o		X ^p	
Drug Administration									
TGR-1202 800 mg		X	→	→	→	→	→		
Toxicity Assessment		X	X	X	X	X		X	X
Correlative Studies									
Blood for PK		X ⁱ		X ⁱ			X ⁱ		
Blood for PD		X ^h		X ^h			X ^h		
Buccal swab	X ^l					X _{l,p}	X ^p		
Lymph Node/Bone Marrow Biopsy	X ^a					X _{l,p}	X ^p		

- a. To be done within 4 weeks of treatment start date.
- b. To be done within 1 week of treatment start date. Nurse practitioner can perform exams after cycle 1.
- c. Chemistries include: Chem *, Mg, K, Hepatic Function Panel, and LDH.
- d. To be done within 1 week of treatment start date for patients of childbearing age.
- e. Not necessary if conducted within 72 hours of screening assessment.
- f. CT scan of the neck, chest, abdomen, and pelvis (and/or PET/CT) at the end of Cycle 2 and 6. Thereafter, restaging CT scans will be repeated every 4 months, or every 6 months if a complete response is achieved. To be performed on every cycle.
- g. Sodium, potassium, chloride, calcium, and glucose are part of the electrolyte assessment at every time point.
- h. Pre-treatment on C1D1, and 4 hours post-treatment on C1D1, C1D15, C2D15 and C4D15
- i. Pre-treatment on C1D1, and 4 hours post-treatment on C1D1, C1D15, C2D15 and C4D15
- j. To be done within 4 weeks of treatment stop date.
- k. To be performed pre-treatment and 4-8 hours post-treatment on C2D15 (mandatory), and C4D15, end of treatment and progression of disease, if applicable (optional).
- l. May be done +/- 7 days.
- m. May be done +/- 3 days.
- n. To be performed after cycle 2 to confirm response if positive at baseline.

- o. If positive at baseline and hasn't been performed to confirm CR
- p. Optional collection of buccal fibroblasts, bone marrow, and Lymph Node Biopsy will be allowed post-treatment on C4D15, at Progression of Disease, and at End of Treatment.

(All study assessments allow a +/- 3 day window)

11. MEASUREMENT OF EFFECT

The primary objective of this study is to evaluate the ORR of the study drug. Patients with measurable disease will be assessed by standard criteria. Patients will be re-evaluated at the end of cycle 2 and cycle 6, thereafter every 4 months, or every 6 months if a CR is achieved. Response will be evaluated with physical exam, computerized tomography (CT) and tissue biopsies as defined in the 2014 Lugano classification.(Cheson et al., 2014b) PET/CT is optional, but strongly encouraged.

Evaluation of response:

Definitions

Evaluable for toxicity: All patients will be evaluable for toxicity starting from Day 1 of Cycle 1.

Evaluable for objective response: Patients who have received at least 1 cycle of therapy, and have had their disease re-evaluated will be considered evaluable for response. These patients will have their response classified according to the definitions stated below (Table 3). Patients who exhibit objective disease progression prior to the end of cycle 1 will also be considered.

Disease Parameters

Measurable disease. Measurable lesions are defined as those that can be accurately measured in two dimensions (longest diameter to be recorded) as ≥ 20 mm with conventional techniques (PET/CT, MRI, x-ray) or as ≥ 10 mm with spiral CT scan. All tumor measurements will be recorded in millimeters (or decimal fractions of centimeters). Tumor volume will be recorded as the sum of the product of the diameters (SPD) of the largest predominant target lesions (for sites of measurable disease, see Appendix 7).

FDG avidity is based on comparison with background tissues. There is no specific SUV cut-off value that is considered indicative of response.

Non-measurable disease (evaluable disease). All other lesions (or sites of disease), including small lesions (<10 mm using spiral CT scan), are considered non-measurable disease. Bone lesions, ascites, pleural/pericardial effusions, lymphangitis cutis/pneumonitis, inflammatory breast disease, abdominal masses (not followed by CT or MRI), and cystic lesions are all nonmeasurable.

Target lesions. All measurable lesions, up to a maximum of 6, that are representative of all involved organs, should be identified as target lesions and measured and recorded at baseline. If PET/CT is performed, target lesions should be selected on the basis of their FDG avidity (High SUV lesions will be prioritized, even if not the largest lesions), size (lesions with the largest SPD diameter) and their suitability for accurate repeated measurements (either by imaging techniques or clinically). An SPD for all target lesions will be calculated and reported as the baseline sum SPD. The baseline sum SPD will be used as reference by which to characterize the objective tumor response based on CT criteria.

Non-target lesions. All other lesions (or sites of disease) including any measurable lesions over and above the 6 target lesions should be identified as non-target lesions and should also be recorded at baseline. Measurements of these lesions are not required, but the presence or absence of each should be noted throughout follow-up.

Methods for Evaluation of Measurable Disease in NHL

All measurements should be taken and recorded in metric notation using a ruler or calipers. All baseline evaluations should be performed as closely as possible to the beginning of treatment and never more than 4 weeks before the beginning of the treatment.

The same method of assessment and the same technique should be used to characterize each identified and reported lesion at baseline and during follow-up. As a general rule imaging-based evaluation is preferred to evaluation by clinical examination when both methods have been used to assess the antitumor effect of a treatment.

Clinical lesions. Clinical lesions will only be considered measurable when they are superficial (e.g., skin nodules and palpable lymph nodes). In the case of skin lesions, documentation by color medical photography that includes a ruler to measure the size of the lesion, is recommended.

CT, PET/CT and MRI. These techniques should be performed with cuts of 10 mm or less in slice thickness contiguously. Spiral CT should be performed using a 5 mm contiguous reconstruction algorithm. This applies to tumors of the chest, abdomen, and pelvis. Imaging of head and neck tumors and those of the extremities will be performed according to institutional specific protocols.

Ultrasound (US) Will not be used for disease assessment

Response Criteria

Response assessment in NHL

Responses will be evaluated using clinical parameters, CT scan (PET scan is optional) and bone marrow biopsy according to the 2014 Lugano Classification (Cheson et al., 2014a) as outlined in Table 3.

Table 3. Revised Criteria for Response Assessment (Cheson et al., JCO 2014)

Complete	Complete metabolic response	Complete radiologic response (all of the following):
----------	-----------------------------	--

Lymph nodes and extralymphatic sites	Score 1, 2, or 3* with or without a residual mass on 5PS† It is recognized that in Waldeyer's ring or extranodal sites with high physiologic uptake or with activation within spleen or marrow (eg, with chemotherapy or myeloid colony-stimulating factors), uptake may be	Target nodes/nodal masses must regress to ≤ 1.5 cm in LD _i . No extralymphatic sites of disease
--------------------------------------	--	---

	greater than normal mediastinum and/or liver. In this circumstance, complete metabolic response may be inferred if uptake at sites of initial involvement is no greater than surrounding normal tissue even if the tissue has high physiologic uptake	
Nonmeasured lesion	Not applicable	Absent
Organ enlargement	Not applicable	Regress to normal
New lesions	None	None
Bone marrow	No evidence of FDG-avid disease in marrow	Normal by morphology; if indeterminate, IHC negative
Partial	Partial metabolic response	Partial remission (all of the following):
Lymph nodes and extralymphatic sites	Score 4 or 5† with reduced uptake compared with baseline and residual mass(es) of any size	$\geq 50\%$ decrease in SPD of up to 6 target measurable nodes and extranodal sites
Non-measured lesion	At interim, these findings suggest responding disease	When a lesion is too small to measure on CT, assign 5 mm x 5 mm as the default value
Organ enlargement	At end of treatment, these findings indicate residual disease	When no longer visible, 0 x 0 mm. For a node > 5 mm x 5 mm, but smaller than normal, use actual measurement for calculation
New lesions	None	None
Bone marrow	Residual uptake higher than uptake in normal marrow but reduced compared with baseline (diffuse uptake compatible with reactive changes from chemotherapy allowed). If there are persistent focal changes in the marrow in the context of a nodal response, consideration should be given to further evaluation with MRI or biopsy or an interval scan	Not applicable
No response or stable disease	No metabolic response	Stable disease:
Target nodes/nodal masses, extranodal lesions	Score 4 or 5 with no significant change in FDG uptake from baseline at interim or end of treatment	
 - $\leq 50\%$ decrease from baseline in SPD of up to 6 dominant, measurable nodes and extranodal sites; - no criteria for progressive disease are met
Non-measured lesion	Not applicable	No increase consistent with progression
Organ enlargement	Not applicable	No increase consistent with progression
New lesions	None	None
Bone marrow	No change from baseline	Not applicable
Progressive disease	Progressive metabolic disease	Progressive disease requires at least 1 of the following:
Individual target nodes/nodal Masses	Score 4 or 5 with an increase in intensity of uptake from baseline and/or	PPD progression

Extranodal lesions	New FDG-avid foci consistent with lymphoma at interim or end-of-treatment assessment	An individual node/lesion must be abnormal with: 
 - $LDi > 1.5$ cm and - Increase by $\geq 50\%$ from PPD nadir and - An increase in LDi or SDi from nadir - 0.5 cm for lesions ≤ 2 cm - 1.0 cm for lesions > 2 cm 
In the setting of splenomegaly, the splenic length must increase by $> 50\%$ of the extent of its prior increase beyond baseline (eg, a 15-cm spleen must increase to > 16 cm). If no prior splenomegaly, must increase by at least 2 cm from baseline. New or recurrent splenomegaly

Non-measured lesion	None	New or clear progression of preexisting non measured lesions
New lesions	New FDG-avid foci consistent with lymphoma rather than another etiology (eg, infection, inflammation). If	
 - Regrowth of previously resolved lesions - A new node > 1.5 cm in any axis
	uncertain regarding etiology of new lesions, biopsy or interval scan may be considered	
 - A new extranodal site > 1.0 cm in any axis; if > 1.0 cm in any axis, its presence must be unequivocal and must be attributable to lymphoma - Assessable disease of any size unequivocally attributable to lymphoma
Bone marrow	New or recurrent FDG-avid foci	New or recurrent involvement

Abbreviations: 5PS, 5-point scale; CT, computed tomography; FDG, fluorodeoxyglucose; IHC, immunohistochemistry; LDi, longest transverse diameter of a lesion; MRI, magnetic resonance imaging; PET, positron emission tomography; PPD, cross product of the LDi and perpendicular diameter; SDi, shortest axis perpendicular to the LDi; SPD, sum of the product of the perpendicular diameters for multiple lesions.

* A score of 3 in many patients indicates a good prognosis with standard treatment, especially if at the time of an interim scan. However, in trials involving PET where de-escalation is investigated, it may be preferable to consider a score of 3 as inadequate response (to avoid under treatment). Measured dominant lesions: Up to six of the largest dominant nodes, nodal masses, and extranodal lesions selected to be clearly measurable in two diameters. Nodes should preferably be from disparate regions of the body and should include, where applicable, mediastinal and retroperitoneal areas. Non-nodal lesions include those in solid organs (eg, liver, spleen, kidneys, lungs), GI involvement, cutaneous lesions, or those noted on palpation. Nonmeasured lesions: Any disease not selected as measured, dominant disease and truly assessable disease should be considered not measured. These sites include any nodes, nodal masses, and extranodal sites not selected as dominant or measurable or that do not meet the requirements for measurability but are still considered abnormal, as well as truly assessable disease, which is any site of suspected disease that would be difficult to follow quantitatively with measurement, including pleural effusions, ascites, bone lesions, leptomeningeal disease, abdominal masses, and other lesions that cannot be confirmed and followed by imaging. In Waldeyer's ring or in extranodal sites (eg, GI tract, liver, bone marrow), FDG uptake may be greater than in the mediastinum with complete metabolic response, but should be no higher than surrounding normal physiologic uptake (eg, with marrow activation as a result of chemotherapy or myeloid growth factors).

†PET 5PS: 1, no uptake above background; 2, uptake \leq mediastinum; 3, uptake $>$ mediastinum but \leq liver; 4, uptake moderately $>$ liver; 5, uptake markedly higher than liver and/or new lesions; X, new areas of uptake unlikely to be related to lymphoma.

Overall Response Rate

Overall Response Rate (ORR) will be defined as the sum of CR rate and PR rate based on evaluation of best response in each patient.

Evaluation of Best Response

The best overall response is the best response recorded from the start of the treatment until disease progression/recurrence. The patient's best response assignment will depend on the achievement of both measurement and confirmation criteria. The best overall response will be used as the reference to define progression of disease, should this occur.

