- 4) Relapse following first line immunotherapy or chemoimmunotherapy. There is no upper limit to the number of therapies received prior to study entry. Prior therapies may include high-dose therapy with autologous stem cell rescue.
- 5) Measurable Disease according to the Lugano classification (Cheson et al., 2014a). See Appendices 1 and 2.
- 6) Lymphoma that is amenable to safe pre-treatment and post-treatment biopsy. The safety of the procedures will be determined by the treating physician and the surgeon (or other proceduralist) in consultation with the PI, and in accordance with standard clinical practice. Acceptable sites of disease include, for example: (1) palpable tumor mass that is accessible under direct visualization or sonogram, (2) non-palpable tumor tissue that is accessible for biopsy under CT or sonogram guidance, (3) bone marrow.
- 7) Age ≥ 18 years
- 8) ECOG performance status ≤ 2 (see Appendix 3).
- 9) Patients must have adequate organ and marrow function as defined below:
 - a. absolute neutrophil count $\geq 1,000/\text{microliter}$
 - b. platelet count $\geq 50,000/\text{microliter}$
 - c. bilirubin $\leq 1.5X$ institutional upper limit of normal
 - d. aspartate transaminase (AST, SGOT)/alanine transaminase (ALT, SGPT) $\leq 3.0X$ institutional upper limit of normal
 - e. Serum creatinine $\leq 2.0X$ institutional upper limit of normal or creatinine clearance $\geq 50 \text{ mL/min}$ (according to the Cockroft and Gault equation).
- 10) Negative serum pregnancy test within 7 days prior to Cycle 1/Day 1 for women of childbearing potential.
- 11) All women of childbearing potential must agree to use an effective barrier method of contraception, as described in Appendix 4, during the treatment period and for at least 1 month after discontinuation of the study drug. Male subjects should use effective barrier method of contraception during the treatment period and for at least 1 month after discontinuation of the study drug (see Appendix 4).
- 12) Ability to understand and the willingness to sign a written informed consent document.

Exclusion Criteria

- 1) Grade 3B FL or evidence of transformation to a more aggressive lymphoma
- 2) Prior and concomitant therapy:
 - a. Prior exposure to any PI3 Kinase inhibitor
 - b. Exposure to chemotherapy, radiotherapy, or immunotherapy within 3 weeks prior to entering the study or lack of recovery from adverse events (AE) due to previously administered treatments.

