3. PATIENT SELECTION

Inclusion Criteria

1. Histologically proven diagnosis of grade 1, 2, or 3A FL
2. The diagnosis of relapsed FL must have been made within the last 6 months of screening if no other treatment is given for the FL in the interim; if an interim treatment is given within the last 6 month, re-biopsy will be required even if there is already a biopsy proven relapsed FL within the last 6 months.
3. Pre-treatment biopsy must establish the diagnosis AND have enough remaining tissues to satisfy the mandatory research studies.
4. Relapse following first line immunotherapy or chemoimmunotherapy. There is no upper limit to the number of therapies received prior to study entry. Prior therapies may include high-dose therapy with autologous stem cell rescue.
5. Measurable disease according to the Lugano classification (Cheson et al., 2014a). See Appendices 1 and 2.
6. Lymphoma that is amenable to safe pre-treatment and post-treatment biopsy. The safety of the procedures will be determined by the treating physician and the surgeon or other proceduralist, in consultation with the PI, and in accordance with standard clinical practice. Acceptable sites of disease include, for example: (1) palpable tumor mass that is accessible under direct visualization or sonogram, (2) non-palpable tumor tissue that is accessible for biopsy under CT or sonogram guidance, (3) bone marrow.
7. Age ≥ 18 years.
8. ECOG performance status ≤ 2 (see Appendix 3)
9. Patients must have adequate organ and marrow function as defined below:
 - a. absolute neutrophil count $\geq 1,000/\text{microliter}$
 - b. platelet count $\geq 50,000/\text{microliter}$
 - c. bilirubin $\leq 1.5X$ institutional upper limit of normal
 - d. aspartate transaminase (AST, SGOT)/alanine transaminase (ALT, SGPT) $\leq 3.0X$ institutional upper limit of normal
 - e. Serum creatinine $\leq 2.0X$ institutional upper limit of normal or creatinine clearance $\geq 50 \text{ mL/min}$ (according to the Cockcroft and Gault equation).
10. Negative serum pregnancy test within 7 days prior to Cycle 1/Day 1 for women of childbearing potential

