Appendix 2. Revised Staging System for Primary Nodal Lymphoma

Stage	Involvement	Extranodal (E) Status
Limited		
I	One node or a group of adjacent nodes	Single extranodal lesions without nodal involvement
II	Two or more nodal groups on the same side of the diaphragm	Stage I or II by nodal extent with limited contiguous extranodal involvement
II bulky*	II as above with "bulky" disease	Not applicable
Advanced		
III	Nodes on both sides of the diaphragm; nodes above the diaphragm with spleen involvement	Not applicable
IV	Additional noncontiguous extralymphatic involvement	Not applicable

* A variety of sizes have been suggested for the definition of bulky disease in NHL. However, none of the proposed sizes have been validated in the current therapeutic era. Therefore, it is recommended to record the longest measurement by CT scan. Whether stage II bulky disease is treated as limited or advanced disease may be determined by histology and a number of prognostic factors.

NOTE. Extent of disease is determined by positron emission tomography-computed tomography for avid lymphomas and computed tomography for nonavid histologies. Tonsils, Waldeyer's ring, and spleen are considered nodal tissue.

Adapted from: Cheson BD, Fisher RI, Barrington SF, et al. J Clin Oncol. 2014;32:3059-3067

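### Section 11 lets a 10–15 mm node on spiral CT be a target lesion, although Table 3 already places a node of that size within the complete-response limit

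*Combined protocol and SAP*

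**What the plan says.** **Measurability.** Section 11, under Disease Parameters, gives the size rule: "as ≥ 20 mm with conventional techniques (PET/CT, MRI, x-ray) or as ≥ 10 mm with spiral CT scan". The next definition confirms the lower limit: other lesions, "including small lesions (<10 mm using spiral CT scan), are considered non-measurable disease". Nodes have no minimum of their own.

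**Target lesions.** Section 11 takes "All measurable lesions, up to a maximum of 6" as targets and adds no further size floor.

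**Response on CT.** For complete radiologic response, the node row of Table 3 reads "Target nodes/nodal masses must regress to ≤ 1.5 cm" (longest diameter). It asks for no percentage decrease. Partial remission needs an SPD decrease of at least 50%. Stable disease is an SPD decrease of no more than 50% with no progression criterion met. Both a progressing node and a new node must exceed 1.5 cm.

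**Which column applies.** Section 11 states that "PET/CT is optional, but strongly encouraged", so some patients may be read by CT alone.

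**Eligibility.** Inclusion criterion 5 in Section 3 asks for "Measurable disease according to the Lugano classification", as does the Synopsis. It cites the publication and Appendices 1 and 2. Neither appendix gives a minimum lesion size; the only remark on size in Appendix 2 concerns bulky disease ("A variety of sizes have been suggested for the definition of bulky disease in NHL").

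**Endpoint.** ORR is CR plus partial remission by best response. Section 13 plans 20 patients, with ORR 0.33 against 0.60, one-sided type I error 0.10 and power 87%.

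**The concern.** Section 11 and Table 3 use different size boundaries for a node. A node of 10–15 mm is large enough to be followed as disease under Section 11, yet small enough to satisfy the nodal size for CR under Table 3 before treatment starts. After a trivial decrease, the CT rules place it in two categories at once, and the plan does not say which prevails. One category counts as a response and the other does not, so the classification of such a patient on the primary endpoint would depend on the reader.

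**Working it through.** **1. The plan's own figure.** Section 13 gives n = 20, null ORR 0.33, alternative 0.60 and one-sided alpha 0.10. It states no cut-off, so I derived one with exact binomial tails:

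- P(Bin(20, 0.33) ≥ 9) = 0.1818, above 0.10.
- P(Bin(20, 0.33) ≥ 10) = 0.0866, within 0.10.
- P(Bin(20, 0.60) ≥ 10) = 0.8725, which matches the stated 87%.

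The design figure reproduces with a cut-off of 10 responders in 20. It is not in dispute.

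**2. The two size rules side by side.**

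| Rule | Source | Boundary for a node on CT |
|---|---|---|
| Measurable, can be a target | Section 11 | ≥ 10 mm (spiral CT) |
| CR, node row | Table 3 | ≤ 15 mm |
| Progressing or new node | Table 3 | > 15 mm |

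Nodes from 10 to 15 mm satisfy the first two rows together at baseline.

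**3. Small changes scored by the CT column.** SPD is the longest diameter times the perpendicular one, and the decrease is 1 − (follow-up SPD ÷ baseline SPD).

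| Baseline (mm) | Follow-up (mm) | SPD (mm²) | Decrease | CR node size met | PR met | Stable-disease SPD rule met |
|---|---|---|---|---|---|---|
| 15 × 15 | 14 × 14 | 225 → 196 | 12.9% | yes | no | yes |
| 14 × 12 | 13 × 12 | 168 → 156 | 7.1% | yes | no | yes |
| 16 × 12 | 15 × 12 | 192 → 180 | 6.25% | yes | no | yes |
| 20 × 15 | 15 × 15 | 300 → 225 | 25.0% | yes | no | yes |

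The first two rows exist only because Section 11 admits nodes of 15 mm or less as targets. The last two start above 1.5 cm and still fit both categories. That overlap comes from Table 3 itself, which pairs an absolute size for CR with a percentage rule for stable disease. Raising the target threshold removes the first kind of case but not the second.

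**4. Illustration of the stakes.** The documents do not say how many patients would be affected or how they would be scored, so this step rests on assumptions. One patient in 20 moves the observed ORR by 1/20 = 5 points. Suppose exactly one patient is scored CR with probability q whatever the drug does, and the other 19 respond at 0.33. Then

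P(≥ 10 responders) = q × P(Bin(19, 0.33) ≥ 9) + (1 − q) × P(Bin(19, 0.33) ≥ 10) = q × 0.1389 + (1 − q) × 0.0608.

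| q | Type I error |
|---|---|
| 0 | 0.0608 |
| 0.33 | 0.0866 (as designed) |
| 0.5 | 0.0999 |
| 1 | 0.1389 |

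The error passes 0.10 only when q exceeds about 0.502. With no such patient, or if the patient is scored as stable disease, there is no inflation.

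**The case against.** The strongest reply is that the situation hardly arises. CT-based CR needs every row of Table 3: no extralymphatic disease, non-measured lesions absent, organs of normal size, no new lesions and normal marrow. All of the patient's target nodes must be 1.5 cm or less, although the Table 3 footnote favours the largest lesions. The lymphoma must also be amenable to mandatory biopsy before treatment and on C2D15. If the biopsied site is involved marrow, CR requires that marrow to become normal. If PET is used, unchanged uptake at score 4 or 5 is no metabolic response. All of this stands, and it is why the reach is small.

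A second reply is that inclusion criterion 5 defers to Lugano, so patients with only 10–15 mm nodes might never enrol. The documents cannot settle this, because they give no Lugano figure for measurability. For the same reason, a reader might infer that Section 11 contradicts Lugano, but the documents do not support that. What they show is a mismatch between Section 11 and Table 3.

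A third reply is that the node row speaks of regression to the limit, which can be read as requiring a start above it. On that reading a node that stays at 14 mm is not a CR, and a reader who infers that unchanged nodes would be scored as CR goes further than the text. The wording does not, however, clearly exclude a node that shrinks from 15 to 14 mm. The section on best response also mentions confirmation criteria, but it does not define them for lesion size.

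Finally, a reader might infer that the 10 mm threshold causes the whole overlap between CR and stable disease. It does not: the 16 × 12 mm example shows that part of it lies within Table 3.

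**Conclusion.** The mismatch is real and follows from the protocol's text alone. Section 11 admits nodal targets of 10–15 mm on spiral CT that already lie within the CR size of Table 3, and after a trivial decrease such a node meets both the CR node row and the stable-disease SPD rule.

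The affected group needs all of the following: response read by CT alone, every target node at 1.5 cm or less, every other CR row met, disease still suitable for the mandatory biopsies, and enrolment under inclusion criterion 5. Its size is unknown and may be zero. It would be tempting to conclude that the ORR will be inflated or that type I error exceeds 10%. The documents do not support that: the calculation assumes one affected patient, a chosen q and a derived cut-off, while the analysis that Section 13 describes is the ORR with exact 95% confidence intervals.

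Severity is minor. Confidence is high on the mismatch and low on its effect.

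**What to change.** In Section 11, require a nodal target lesion on CT to have a longest diameter above 1.5 cm at baseline, as in Table 3. In the same edit, state:

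- that inclusion criterion 5 uses this definition;
- whether the 20 mm threshold for PET/CT, MRI and x-ray stays, so that a 16–19 mm node is not left unclear;
- that nodes of 1.5 cm or less are not non-measured lesions for the *Absent* row of CR. Otherwise a node barred from being a target might have to vanish before CR could be recorded.

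Add one sentence to Table 3 saying which category prevails when a patient meets both CR and stable disease. The new threshold alone does not settle nodes that start just above 1.5 cm.

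A scoring rule that a node of 1.5 cm or less at baseline cannot support CR would leave eligibility alone, but it is less sound. It would deny a CT-based CR even when the node disappears, and CR status sets the later scan interval (6 rather than 4 months). It would also leave patients with both small and large nodes unclear.

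The cost is a few sentences, with no change to sample size or power. The downside is that a few patients with only small nodes might not count as having measurable disease.
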